6 PLANNED ANALYSES

No statistical analysis plan (SAP) prepared in advance of the data can be absolutely definitive and the final Clinical Study Report (CSR) may contain additional tables or statistical tests if warranted by the efficacy and safety data results. The justification for any such additional analyses will be fully documented in the final CSR.

6.1 Analysis Sets

6.1.1 Safety Analysis Population

The safety analysis population will contain all Participants who sign the Informed Consent of the VMALS-002-2b study. Participants will be grouped according to their actual treatment received in VMALS-002-2 study.

6.2 Derived Data

6.2.1 Race

Where more than one race category has been selected for a subject, these race categories will be combined into a single category labeled “Multiple Race” in the summary tables. The listings will reflect the original selected categories.

6.2.2 Baseline

Baseline is defined as the last non-missing value (either scheduled, unscheduled or repeat) before the participant receives first Study Injection in the Study VMALS-002-2.

6.2.3 Duration / Study Day / Time

Study day will be calculated as the number of days from first Study Injection in the Study VMALS-002-2:

- date of event – date of first Study Injection + 1, for events on or after first Study Injection in the Study VMALS-002-2
- date of event – date of first Study Injection, for events before first Study Injection in the Study VMALS-002-2

Duration of ALS diagnosis will be presented in months and calculated as (Date of Screening of the Study VMALS-002-2 – Date of Onset of Symptoms +1) / 30.4375.

QMD Ref: Worldwide-TMP-ST-005-7.0 Effective: 12Aug2019	Governing QMD: Worldwide-SOP-ST-001
Confidentiality Statement	

This document is the property of Worldwide Clinical Trials Inc. and may not be duplicated, copied, altered or removed from company without prior approval from Worldwide Quality Assurance or in compliance with Worldwide Standard Operating Procedures.

Worldwide Clinical Trials Controlled Quality Management Document			
 WORLDWIDE CLINICAL TRIALS	Sponsor:	Helixmith Co., Ltd.	
	Protocol Number:	VMALS-002-2b	
STATISTICAL ANALYSIS PLAN. PHASE 2-3-4			

Time to tracheostomy will be calculated as time from date of first Study Injection in the VMALS-002-2 Study to date of first occurrence of ALSFRS-R questionnaire with answer “**0 - Invasive mechanical ventilation by intubation or tracheostomy**” to question “**12. Respiratory insufficiency**” (ASLFRS-R date – date of the first injection +1) presented in days.

Time to all-cause mortality will be calculated as the time period from date of first Study Drug Injection in the Study VMALS-002-2 to date of death within 365 days presented in days (death date – date of the first injection +1).

Both time-to-event endpoints will be censored by date of last visit.

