2.2.6.1. Phase 1/2 Study in Participants with Amyotrophic Lateral Sclerosis

A Phase 1/2, open label, single center study in 18 Participants diagnosed with clinically definite, clinically probable, or clinically probable-laboratory supported ALS (VMALS-001; NCT02039401) lasting 9 months was completed.⁶¹ Prior to injections on Day 0, Participants were assessed using the ALSFRS-R, the Medical Research Council (MRC) scale for muscle strength testing, dynamometry, forced vital capacity (FVC), and muscle circumference of treated muscles.

All Participants (18 Participants) received a total of 64 mg of Engensis IM in the upper limbs (abductor pollicis brevis, first dorsal interosseous, biceps, deltoid, extensor carpi radialis, flexor carpi ulnaris, and flexor carpi radialis) and lower limbs (quadriceps, gastrocnemius, and tibialis anterior).

Engensis was administered over the course of four visits: Days 0, 7, 14, and 30. As in previous Engensis studies, the final dose of Engensis for each target muscle group was divided and administered 2 weeks apart with injection of the upper limbs at separate visits followed by injection of the lower limbs.

Post-injection, ALSFRS-R, FVC, and muscle strength (determined by the MRC scale) were assessed at Days 30, 60, and 90, and at 6 and 9 months. Muscle circumference and dynamometry were conducted on Days 60 and 90, and at 6 and 9 months. Participants were contacted through 36 months by phone to assess survival.

After Engensis or Placebo injections through Day 30, seventeen (17) Participants completed the 9-month follow-up; one Participant died prior to the 9-month visit. Three (3) Participants completed the study (36-month follow-up), while 14 Participants died following the 9-month visit; all deceased Participants died due to respiratory failure associated with ALS. Four additional serious adverse events (SAEs) that required hospitalization were reported. All deaths and SAEs were classified as unrelated to the study drug. Injection site reactions were limited to pain and/or bruising and none exceeded grade 2 severity.

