7.2. Lost to Follow-up

A Participant will be considered lost to follow-up if he or she repeatedly fails to return for scheduled Visits and is unable to be contacted by the Site between the Day 180 of VMALS-002-2 and the Day 365 (+7 days) of VMALS-002-2b.

The following actions must be taken and recorded if a Participant fails to return to the clinic for a required study Visit:

- The site must attempt to contact the Participant and reschedule the missed Visit as soon as possible. The site must counsel the Participant on the importance of

maintaining the assigned Visit schedule and ascertain whether or not the Participant wishes to and/or should continue in the study.

- If no response is obtained from the Participant, the Investigator is encouraged to contact one of the Participant's relatives or his/her general practitioner.
- Before a Participant is deemed lost to follow up, the Investigator or designee must make every effort to regain contact with the Participant, including at least three telephone calls and, finally, a certified letter to the Participant's last known mailing address. These contact attempts should be documented in the source records.
- Should the Participant continue to be unreachable, the Participant will be considered lost to follow-up.

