8.3.1. Time Period and Frequency for Collecting TEAE and TESAE Information

All TEAEs and TESAEs will be collected after signing informed consent prior to, on, or after Day 180 of the Study VMALS-002-2 until the time that the Participant completes or withdraws consent for VMALS-002-2b (see definition of TEAE, Section [10.2](#)).

All TESAEs will be recorded and reported to the Sponsor or designee immediately and under no circumstance should this exceed 24 hours, as indicated in Section [10.2.5](#), Appendix 2. The Investigator will submit any updated TESAE data to the Sponsor within 24 hours of its availability.

Investigators are not obligated to actively seek TEAEs or TESAEs after conclusion of the study participation. However, if the Investigator learns of any TESAE, including a death, at any time after a Participant has been discontinued from the study, and he/she considers the event to be possibly, probably, or definitely related to the study intervention or study participation, the Investigator must promptly notify the Sponsor.

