6.15.6 Time to tracheostomy

Time to tracheostomy will be presented with descriptive statistics and corresponding survival curves using Kaplan- Meier analysis (Table 14.6.8, Listing 16.2.9.8).

SAS code example for Kaplan-Meier analysis:

```
proc lifetest data=DATAIN method = km;
  time AVAL*CNSR(1);
  strata TRT01PN / test = logrank;
run;
```

DATAIN – source dataset

AVAL – time to event

CNSR – flag for censoring, if CNSR=1 then the corresponding value of AVAL is a censored value and not an observed event

TRT01PN – treatment group

Analysis will be performed on data combined for core study the Study VMALS-002-2 (Screening, Day 0 pre-dose, Day 30, Day 60 pre-dose, Day 84, Day 120 pre-dose, Day 144 and Day 180) and for this extension study the Study VMALS-002-2b (Day 240, Day 300, Day 365/ET4).

QMD Ref: Worldwide-TMP-ST-005-7.0 Effective: 12Aug2019	Governing QMD: Worldwide-SOP-ST-001
Confidentiality Statement	

This document is the property of Worldwide Clinical Trials Inc. and may not be duplicated, copied, altered or removed from company without prior approval from Worldwide Quality Assurance or in compliance with Worldwide Standard Operating Procedures.

Worldwide Clinical Trials Controlled Quality Management Document			
 WORLDWIDE CLINICAL TRIALS	Sponsor:	Helixmith Co., Ltd.	
	Protocol Number:	VMALS-002-2b	
STATISTICAL ANALYSIS PLAN. PHASE 2-3-4			

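### The 365-day limit on counted deaths, with censoring at the last visit, can turn a known death in the final visit window into a censoring, and no vital status is sought after early termination

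*SAP*

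**What the plan says.** **Endpoint and day count.** The protocol (Sections 1.1 and 3) lists time to all-cause mortality as an exploratory endpoint and sets no time limit on it. SAP 6.2.3 runs the time from first injection "to date of death within 365 days presented in days" and gives the formula in the same sentence: "death date – date of the first injection +1". The general study-day rule in that section is the same: "date of event – date of first Study Injection + 1, for events on or after first Study Injection". SAP Section 9 declares no change from the protocol's planned analysis.

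**Censoring.** SAP 6.2.3: "Both time-to-event endpoints will be censored by date of last visit". It does not separate participants known to have died from the rest.

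**Final visit.** The Schedule of Activities allows 7 days either side of Day 365. Protocol 7.2 runs the lost-to-follow-up period to "the Day 365 (+7 days) of VMALS-002-2b".

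**After early termination.** Protocol 7.1 plans one termination visit, where possible, and its list contains no later survival contact. Protocol 8.3.1: "Investigators are not obligated to actively seek TEAEs or TESAEs after conclusion of the study participation". A death that the site learns of after discontinuation must be notified only if the investigator considers it related. Protocol 10.2.2 gives death from disease progression as an example of an event that cannot be a TESAE.

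**Earlier ALS study.** Protocol 2.2.6.1, on VMALS-001: "Participants were contacted through 36 months by phone to assess survival".

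**The concern.** There are two separate weaknesses.

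First, the event limit and the censoring rule use different end points. Deaths stop counting at 365, but a survivor is followed to the final visit, which may fall later. Someone who dies while waiting for an in-window final visit has no such visit. If the death falls past the limit, it is not an event, and the participant drops back to the preceding visit as a censored survivor. The analysis then misstates something the trial already knows.

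Second, for a participant who terminates early, nothing in the plan looks for a death between the last visit and Day 365. Adverse events and the investigator's own decision are listed reasons for leaving (Protocol 7.1). In ALS, departure may go with decline, in which case censoring at the last visit is informative.

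With at most 18 participants, one death visibly moves a Kaplan-Meier curve.

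**Working it through.** The plan gives no event count, power or dropout rate, so there is no figure of its own to reproduce.

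**1. Day count.** Value = elapsed days since first injection + 1. I take the first injection to be on Day 0. This rests on the visit labels in SAP 6.15.6, "Screening, Day 0 pre-dose, Day 30, Day 60 pre-dose"; the parent protocol is not available.

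| Visit or date | Elapsed day | SAP value |
|---|---|---|
| First injection | 0 | 1 |
| Day 300 | 300 | 301 |
| Window opens | 358 | 359 |
| Last counted death (limit of 365 on the SAP value) | 364 | 365 |
| Nominal Day 365 visit | 365 | 366 |
| Window closes | 372 | 373 |

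The window has 15 permitted days, and 8 of them (values 366 to 373) lie beyond the limit. If the limit means elapsed days, it coincides with the nominal visit and 7 of the 15 (elapsed 366 to 372) lie beyond it. A participant last seen at Day 300 who dies at value 366 is censored at 301: the death is lost, and so are about 65 days of known survival.

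**2. Assumed hazards, for scale only.** VMALS-001 (Protocol 2.2.6.1): 1 of 18 died before month 9, and 14 of the remaining 17 died by month 36. With a constant hazard within each period:

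- Low: −ln(17/18)/9 = 0.0064 per month
- High: −ln(3/17)/27 = 0.064 per month

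**3. Unseen death by Day 365, per early leaver.** Risk = 1 − exp(−h × days/30.4375).

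- Leaving at Day 240 (125 days): 2.6% to 23%
- Leaving at Day 300 (65 days): 1.3% to 13%

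These are risks per person. The trial-level effect needs the number of leavers, which the documents do not give.

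**4. At least one death in the 8 excluded days.** Take 18 (the cap) alive at Day 180 and allow for deaths over the 185 days to Day 365.

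- Surviving fraction, exp(−h × 185/30.4375): 0.96 (low) and 0.68 (high)
- Still at risk at Day 365: 17.3 and 12.2
- Expected deaths, at risk × h × 8/30.4375: 0.029 and 0.206
- Chance of at least one, 1 − exp(−expected): about 3% and 19%

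This is an upper bound, because it needs every final visit to fall on the last permitted day. If visit days are uniform over values 359 to 373, the mean time beyond 365 is (1 + 2 + … + 8)/15 = 36/15 = 2.4 days. Expected deaths become 0.0087 and 0.062, and the chance is about 1% to 6%.

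**The case against.** **The limit may be sound.** A fixed one-year horizon is legitimate, and SAP 6.2.3 attaches the +1 to the reported duration without saying that the limit uses it. Protocol 10.3.2 adds that visit labels are not nth-day counts. This stands as far as it goes: the cut costs one nominal day plus the window, or the window days alone on elapsed days. A reader might infer that it drops deaths inside the planned year. The documents do not support that; the affected days are the nominal visit day and those after it. But the SAP does not say which count applies, and on either reading survivors can be followed past the limit.

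**Safety reporting as a cross-check.** A reader might infer that such a death would appear as a fatal TESAE in the listings while missing from the survival curve. Protocol 10.2.1 and 10.2.2 exclude deaths from expected progression from TESAEs, and in VMALS-001 all deceased participants died of ALS-related respiratory failure. That mismatch is therefore not established for the typical death. The same exclusion means that serious-event reporting cannot be relied on to find deaths.

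**Existing safeguards.** Protocol 7.2 requires calls and a certified letter, and encourages contact with relatives or the general practitioner. Protocol 8.3.5 requires adverse events to be followed up, and the DSMB sees pooled mortality (10.1.5.1). These would often reveal a death after a missed visit. The 7.2 steps apply before a participant is declared lost, though, not after one has terminated early, and none of these provisions schedules a survival check at Day 365.

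**Few leavers.** In VMALS-001, 17 of 18 completed 9 months and the other died. This was an open-label, single-center study, so it is only indicative, but it is a fair warning against assuming a large effect.

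**Conclusion.** Both weaknesses stand, for an exploratory endpoint. The primary safety summaries do not depend on it.

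The day cut is small but can misclassify a death that is on record. It covers 8 days on the SAP count or 7 on elapsed days, with at most about a 3% to 19% chance of touching anyone, and about 1% to 6% with visits spread over the window.

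The gap after early termination is the larger one for each person affected: about 2.6% to 23% for someone leaving at Day 240 and 1.3% to 13% at Day 300. A reader might go on to infer that survival will be overstated, more so in the arm that loses more participants. That is possible, but the documents give no dropout figures, so neither its occurrence nor its size is shown.

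The sizes rest on constant hazards borrowed from VMALS-001, on 18 alive at Day 180, and on first injection at Day 0.

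**What to change.** **SAP 6.2.3, before unblinding.** Define the event as any recorded death on or before the end of the Day 365 visit window, whether or not it is classed as a TESAE. State which day count defines that end. Apply censoring only to participants not known to have died, at the date last known alive.

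**Protocol and consent form, by amendment.** For early terminators who do not refuse contact, make one vital-status check at Day 365, by phone or from records. VMALS-001 is a precedent for survival calls, although over a longer follow-up.

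The check should be limited to vital status. SAP 6.2.3 defines tracheostomy by the answer to ALSFRS-R item 12, so a phone or records report of tracheostomy would not fit that endpoint as written.

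**Cost.** The SAP wording costs almost nothing. The check needs IRB approval of the amended consent form, consultation on re-consent (Protocol 10.1.1.2), and minor site effort for a few people. Those who refuse contact remain censored.

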3.2 Exploratory Endpoints

- Change from Baseline (Study VMALS-002-2 Day 0) in total mean Revised Amyotrophic Lateral Sclerosis Function Rating (ALSFRS-R) scores at Day 365 for Engensis compared to Placebo
- Change from Baseline (Study VMALS-002-2 Day 0) in ALSFRS-R subscores for Fine and Gross Motor Functions (sum of scores for items 4 to 9) and for Bulbar Function (sum of scores for items 1 to 3) at Day 365 for Engensis compared to Placebo
- Changes in the slope of the total ALSFRS-R score over time for Engensis compared to Placebo
- Change from Baseline (Study VMALS-002-2 Day 0) in muscle strength assessed bilaterally by Handheld Dynamometry (HHD) in muscles in the upper and lower extremities at Day 365 for Engensis compared to Placebo
- Change from Baseline (Study VMALS-002-2 Day 0) in Quality of Life (QoL) using the ALS Assessment Questionnaire (ALSAQ; with 40 items, ALSAQ 40) on Day 365 for Engensis compared to Placebo
- Patient Global Impression of Change (PGIC) and Clinical Global Impression of Change (CGIC) at Day 365 for Engensis compared to Placebo
- Change from Baseline (Study VMALS-002-2 Day 0) in Slow Vital Capacity (SVC) at Day 365 for Engensis compared to Placebo
- Time to tracheostomy for Engensis
- Time to all-cause mortality compared to Placebo

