6.15.7 Time to all-cause mortality

Time to all-cause mortality will be presented with descriptive statistics and corresponding survival curves using Kaplan-Meier analysis (Table 14.6.9, Listing 16.2.9.8). Analysis will be performed on data combined for core study the Study VMALS-002-2 and for this extension study the Study VMALS-002-2b.

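### The tracheostomy Kaplan-Meier curve treats death as ordinary censoring, so it overstates how many participants have a tracheostomy (minor; exploratory endpoint)

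*SAP*

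**What the plan says.** SAP 6.2.3 measures time to tracheostomy from the first injection in VMALS-002-2 to the "date of first occurrence of ALSFRS-R questionnaire with answer" of 0 to item 12 (invasive ventilation by intubation or tracheostomy). Death is not part of the event. The section closes with one rule for both time-to-event endpoints: "Both time-to-event endpoints will be censored by date of last visit".

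SAP 6.15.6 gives the analysis: "Time to tracheostomy will be presented with descriptive statistics and corresponding survival curves using Kaplan- Meier analysis". Its SAS example has a two-level status, explained as "if CNSR=1 then the corresponding value of AVAL is a censored value and not an observed event", and compares the arms with "strata TRT01PN / test = logrank". Data from the core and extension studies are combined.

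Mortality is analysed separately in SAP 6.15.7: "Time to all-cause mortality will be presented with descriptive statistics and corresponding survival curves using Kaplan-Meier analysis". Neither document mentions a cumulative incidence, a competing event, or a composite of tracheostomy and death.

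On the disease background, Protocol 2.2.6.1 reports for the Phase 1/2 study VMALS-001 that "all deceased Participants died due to respiratory failure associated with ALS".

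**The concern.** The SAP does not say in words that deaths are censored, but its rules leave no other outcome. With only two status values, a participant who dies without a recorded item 12 score of 0 must be coded as censored, at the last visit before death.

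Kaplan-Meier treats a censored participant as still able to have the event later, at the same rate as those still under observation. A participant who has died cannot. So 1-KM estimates the risk of tracheostomy in a hypothetical setting without death (the net risk), whereas a reader will take it as the proportion who had the procedure.

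There is a second question. If respiratory failure drives both death and invasive ventilation, those who die were probably at higher risk of tracheostomy than those who remain. The censoring would then be informative, and the curve would not estimate the net risk cleanly either. Time to tracheostomy is one of the two endpoints for the respiratory objective, so its display should be readable.

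**Working it through.** The plan gives no tracheostomy rate, event count or power for this endpoint, so there is no figure of its own to reproduce. The check compares 1-KM with the cumulative incidence function (CIF) at one year.

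**Inputs**
- Assumed one-year net risks: 20% death with 10% tracheostomy; 30% death with 15% tracheostomy. The documents give no tracheostomy rate.
- Death rates from Protocol 2.2.6.1, taking hazards as constant: 1 of 18 by 9 months gives −ln(17/18)/0.75 = 0.076 per year (7.3% at one year). 15 of 18 by 36 months gives −ln(3/18)/3 = 0.597 per year (45.0% at one year).
- At most 18 participants (SAP 4). The allocation ratio is not stated.

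**Everyone followed from first injection, independent constant hazards**
- h_d = −ln(1 − p_d), h_t = −ln(1 − p_t)
- 1-KM = 1 − exp(−h_t) = p_t
- CIF = h_t/(h_t + h_d) × [1 − exp(−(h_t + h_d))]

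For 20% and 10%: h_d = 0.2231, h_t = 0.1054, so CIF = 0.3207 × (1 − 0.72) = 0.0898. That is 10.0% against 9.0%, or 11% too high in relative terms.

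For 30% and 15%: h_d = 0.3567, h_t = 0.1625, so CIF = 0.3130 × (1 − 0.595) = 0.1268. That is 15.0% against 12.7%, or 18% too high.

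**Only participants who completed Day 180**

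Here no deaths can occur before s = 180/365 = 0.493:
- CIF = [1 − exp(−h_t s)] + exp(−h_t s) × h_t/(h_t + h_d) × [1 − exp(−(h_t + h_d)(1 − s))]

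For 20% and 10%: 0.0506 + 0.9494 × 0.3207 × 0.1534 = 0.0973, so 10.0% against 9.7% (2.7% too high). For 30% and 15% the result is 15.0% against 14.4% (4.3% too high).

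**Range at the VMALS-001 death rates, 10% net tracheostomy risk**

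| Death rate used | 1-KM | CIF, all from first injection | CIF, Day 180 completers |
|---|---|---|---|
| 9-month rate | 10.0% | 9.6% | 9.9% |
| 36-month rate | 10.0% | 7.6% | 9.3% |

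Over net tracheostomy risks of 5% to 20%, with everyone followed from first injection, the overstatement is 0.2 to 0.7 percentage points at the 9-month rate and 1.2 to 4.8 points at the 36-month rate.

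**Direction between arms**

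A simulation of 1,000,000 participants per scenario used the SAP visit days, censoring at the last visit before death, and a tracheostomy hazard of −ln(0.8) per year. The death rate was raised from the 9-month to the 36-month value.
- Independent risks: 1-KM stays at 20.0%.
- Shared gamma frailty (an assumed common susceptibility), variance 1: 1-KM falls from 17.6% to 14.7%. Variance 2: from 16.0% to 11.9%. In each case 1-KM remains above the CIF (17.1% to 12.3%; 15.6% to 10.4%).
- Small numbers can go the other way. Take 9 per arm (assumed), with 2 tracheostomies at Day 300 in each arm, and 3 deaths in one arm censored at Day 240. 1-KM is 2/9 = 22.2% without the deaths and 2/6 = 33.3% with them. The CIF is 22.2% in both.

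**The case against.** The strongest reply has four parts.

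**Stakes.** The endpoint is exploratory and worded "Time to tracheostomy for Engensis", with no placebo comparison. There are at most 18 participants. The log-rank test appears only in example code, with no significance level. With 2 to 8 events, an assumed hazard ratio of 0.5, equal arms and two-sided 0.05, its power is 7% to 16%. All of this stands and keeps the point minor.

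**Visibility.** Mortality has its own curve and shares Listing 16.2.9.8 with tracheostomy, so an excess of deaths would be seen. This also stands, although a second curve does not correct the first.

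**Population.** Extension entry requires completing Day 180 (Protocol 5), and the only analysis set is those who consent to the extension (SAP 6.1.1). On that reading, participants who died before Day 180 are absent, not censored. At the VMALS-001 9-month rate about 18 × [1 − exp(−0.076 × 185/365)] = 0.7 deaths would be expected after Day 180. The combining of data in SAP 6.15.6 does not settle whether core-only participants are added. This stands, and it shrinks the size.

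**Direction.** A reader might infer that an arm with more early deaths will show less tracheostomy, so that a harmful treatment looks better. The documents do not support that as a general statement. The planned curve falls with deaths only if the two risks are positively linked. Protocol 2.2.6.1 makes such a link plausible, but it reports causes of death and no tracheostomy data. Nor does an example such as 3 deaths and no tracheostomies against no deaths and 2 tracheostomies, 9 per arm, show a fault peculiar to Kaplan-Meier. The CIF gives the same 0% against 22%; only the composite reverses it (33% against 22%).

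**Conclusion.** The point holds in a limited form. The planned rules censor deaths, and 1-KM then overstates the incidence of tracheostomy. The size depends on assumed tracheostomy rates, on constant hazards, and on who is analysed. For a 10% net risk and a 20% death risk it is one percentage point if everyone is followed from first injection, and 0.3 of a point among Day 180 completers. The gap is wider if deaths run at the 36-month rate of VMALS-001.

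Informative censoring is plausible but not shown. What can be said about the arms is that unequal deaths may move the curves in either direction, so a difference between them is hard to read. The documents do not establish a bias favouring the arm with more deaths. Severity is minor.

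**What to change.** Keep time to tracheostomy as the protocol endpoint and amend SAP 6.2.3 and 6.15.6 as follows.

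1. Use a three-level status: item 12 score of 0, death without it (timed at the death date), and censored. Censor at the last visit only participants who are alive without the event.
2. Report tracheostomy by arm as a cumulative incidence with death as the competing event (EVENTCODE= in PROC LIFETEST).
3. Add a supportive Kaplan-Meier display of tracheostomy-free survival, counting the first of an item 12 score of 0 or death from any cause. List the two components beside it.
4. State whether VMALS-002-2 participants who did not enter the extension are included.

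The cost is SAP wording, a few lines of code, and one extra table and figure. Death dates are already needed for the mortality endpoint. The downside is that the composite mixes two outcomes, which is why it should stand beside the protocol endpoint and not replace it. SAP 9, which declares no changes from the protocol analysis, should mention the added displays.
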